## **B. Randomized Evaluation of COVID-19 Therapy (RECOVERY): Efficacy of dexamethasone**

The RECOVERY trial, which first reported preliminary results on June 22, 2020, was an open-label, 1:2 randomized controlled trial of 6,425 patients randomized to either 6 mg of DEX daily for 10 days (n = 2,104) or usual care (n = 4,321). Overall, 22.9% of patients assigned to the DEX group died within 28 days of randomization vs. 25.7% of the control arm (rate ratio [RR] of 0.83, 95% CI [0.75, 0.93]). The difference in survival between the two groups varied noticeably when stratified by baseline COVID-19 severity level. While the incidence of death was lower in the DEX group, compared to the usual care group, among patients receiving IMV (RR: 0.64, 95% CI [0.51, 0.81]) and among those receiving supplemental O2 therapy but not IMV (RR: 0.82, 95% CI [0.72, 0.94]), there was no discernable difference among patients who were not receiving any supplemental O2 (RR: 1.19, 95% CI [0.91 to 1.55]) [*RECOVERY 2020*].

The effectiveness of DEX in preventing death among moderate to severe COVID-19 patients has not yet been confirmed or established in routine care, yet DEX utilization has substantially increased in the US since June 2020 [*Action 2021*]. Thus, to evaluate the effectiveness of DEX in preventing death under routine use in a timely manner, we sought to conduct an observational cohort study using US-based real-world data (RWD).

[figure not shown]
In one of the explorations conducted prior to the finalization of this protocol [see *Appendix A.2. Exploration 2*], we compared the distribution of key patient characteristics between a version of our hospitalized US-based RWD study cohort to those reported for the hospitalized UK-based patients randomized in the RECOVERY trial. The RECOVERY trial was a large, pragmatic randomized trial that simplified the data collection process in an effort to minimize the already heavy burden of the pandemic on frontline workers. Exploration of baseline clinical differences between the real-world study and trial populations was therefore limited by the degree of available information for the trial patients. However, among the available RECOVERY trial data, we identified important clinical and demographic differences in the trial population versus this study's populations at baseline.

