## B. Exposure definition

The primary exposure of interest is new (incident) initiation of systemic DEX. DEX exposure is defined with procedure codes (current procedural terminology, CPT-4/healthcare common procedure coding system, HCPCS [*CMS 2020(b)*]), hospital charge codes for the corresponding text strings (e.g., 'dexamethasone', 'decadron'), and drug names referenced from national drug codes (NDC), where there is an absence of evidence of a non-systemic route of administration (e.g., ciprofloxacin 0.3%/dexamethasone 0.1% ear drops are excluded). All available data types with treatment-specific information are used for assessment of DEX exposures, including medical claims, pharmacy claims, and chargemaster records. DEX use is considered "new" if the patient had no record of systemic DEX dispensing or remaining outpatient pharmacy supply during the 90-day *Treatment Washout Window* prior to the cohort entry and up until 1 day prior to treatment index (Day 0, hospital admission date).

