## C. Study population

### 1. Cohort entry

#### Hospitalized Patients with COVID-19:

Patients will enter the cohort upon the admission date of the first qualifying inpatient hospitalization observed in the hospital chargemaster data. The first eligible cohort entry date is **01-April-2020**, the date when the ICD-10 code for COVID-19 diagnosis was added. The last possible cohort entry date will be 60 days prior to the last date of available data [see *Appendix A.5 Exploration 5* for additional detail justifying this design decision].

COVID-19 confirmation was defined as either of the following occurring between 21 days prior to the hospital admission date and the treatment index date, which is described in section C.2. below (inclusive; **Day -21 to Day T**):

- Outpatient medical encounter prior to or on the admission date or diagnosis 'present at admission' with ICD-10-CM diagnosis of U07.1 for COVID-19, virus identified; OR
- positive or presumptive positive SARS-CoV-2 diagnostic laboratory test result

The decision to include either diagnosis or positive laboratory test results was based on an initial exploration [see justification detail in *Appendix A.1. Exploration 1*].

For the DEX+ versus MPRED+ comparison (**Secondary Objective II**), given the increased use of MPRED earlier on in the COVID-19 pandemic, we may consider delaying the cohort entry to start in May or June pending data exploration.

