### 2. Treatment index

#### **Primary Objective -- New users of DEX (DEX+) versus matched non-users of CSI (CSI-):**

From the patients who enter the cohort, new users of DEX between the admission date (*Day 0*) and 1 day prior to discharge date (*Day D-1*) or a maximum period of 21 days after admission (*Day 21*) will be selected. Greater than 80% of the patients who initiated DEX did so within 1 or 2 days of their hospitalization. A sensitivity analysis (SA2) will be conducted to explore initiation dates further. For each new user of DEX, at least 1 patient who has not (yet) used any CSI as of the DEX patient's index date or within the 90-day washout period prior matched on the

criteria defined in Table 2 below will be randomly risk-set sampled (RSS). DEX+ versus CSI-matching ratios of 1:1, 1:2, 1:3, and 1:4 will be considered to select up to 4 non-user referent patients for each exposed, and the ideal ratio will be selected based on the diagnostic criteria [defined below in section *VI.B. Diagnostic phase and checklist*].

RSS matching allows us to proxy the ‘standard of care’ by randomly selecting 1 or more patients who have not initiated DEX from the risk set of patients who are eligible for initiating DEX at the same time [*Li 2001*]. Since the COVID-19 pandemic and treatment of patients with COVID-19 is rapidly changing over time, there is much potential for calendar-time bias. Furthermore, patients prescribed DEX may appreciably differ from those not prescribed DEX. Employing an RSS that matches DEX users and non-users on the date of DEX treatment (in the users) and time since admission will minimize the potential for this bias. Cohort entry month will also be included in the propensity score (PS) calculation to further adjust for time-related biases. Geographic region was considered for the RSS matching criteria. However, during our data explorations, the comparison of baseline balance showed that matching without region yielded better baseline balance than matching with region. Therefore, we removed region from the RSS matching. However, given known regional differences, we still account for region in our propensity score model.

The *treatment index date* (Day T) for patients who are users and for the matched non-user referent patients will be defined by the index date of the matched users.

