### **Secondary Objective I -- New users of DEX (DEX+) versus matched non-users of DEX (DEX-):**

From the patients who enter the cohort, new users of DEX between the admission date (*Day 0*) and 1 day prior to discharge date (*Day D-1*) or a maximum period of 21 days after admission (*Day 21*) will be selected. For each new user of DEX, at least 1 patient who has not (yet) used DEX as of the DEX patient's index date or within the 90-day washout period prior matched on the criteria defined in Table 2 below will be randomly RSS. DEX+ versus DEX- matching ratios of 1:1, 1:2, 1:3, and 1:4 will be considered to select up to 4 non-user referent patients for each exposed, and the ideal ratio will be selected based on the diagnostic criteria [defined below in section *VI.B. Diagnostic phase and checklist*].

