### **Secondary Objective II -- New users of DEX (DEX+) versus new users of MPRED (MPRED):**

From the patients who enter the cohort, all patients who begin use of DEX or MPRED between the admission date (*Day 0*) and 1 day prior to discharge date (*Day D-1*) or a maximum period of 21 days after admission (*Day 21*). New use will be determined using a 90-day washout period to exclude patients with prior use of either DEX or MPRED during the 90 days prior. If a patient uses both treatments over the course of the admission, they will be assigned to their first qualifying treatment arm. If a patient receives both DEX and MPRED on the treatment index, they will be excluded since the effects or the drugs cannot be disentangled among these patients.

*Table 2: Risk set sampling (RSS) matching criteria*

RSS matching criteria	Variable type	Categories (for categorical) / calipers (for continuous)
Calendar date	continuous	±3 days
Age	continuous	±3 years
Sex	categorical	male, female
Combined comorbidity score over 183d baseline period [ Gagne 2011 ]	categorical	0-1, 2-3, 4-5, 6+
Time since hospital admission	categorical	0-1, 2-3, 4-5, 6 - 9, 10 - 14, 15 - 19, 20+ days
COVID-19 severity at treatment index date, per modified WHO (mWHO) score	categorical	No O2, O2/NIV, IMV (highest recorded from days T-1 to T) [see additional subgroup detail below in section V.D. Subgroups ]

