**VI. STATISTICAL METHODS**

**A. Propensity score model fitting**

Propensity score (PS) matching will be used to control for confounding by identifying referent patients who are comparable to DEX+ patients with respect to several covariates identified *a*

*priori* for their potential to introduce confounding. Multivariable logistic regression will be used to estimate the propensity to initiate DEX+ versus each referent group (CSI-; DEX-; MPRED+), based on main effects of the independent covariates without interaction terms. PS model coefficients will be estimated using the overall study cohort. Appropriate referent groups will be identified using nearest neighbor matching with a caliper width of  $\pm 1\%$ . Referent groups for subgroup analyses will be identified using the overall PS model [Wang 2018, Strategy A].

Model fit and performance will be evaluated using the criteria outlined in Table 4. The PS model for the primary objective will be deemed acceptable if all the criteria described in Table 4 are achieved. We will further attempt to satisfy all criteria for secondary objectives, but strategies such as covariate adjustment to control for residual imbalance may be used in the event that some criteria are not satisfied.

As a secondary modeling strategy, we may consider estimating PS model coefficients within each subgroup and pooling subgroup matches to form the overall cohort. This modeling strategy may be used for the final analysis if diagnostic criteria outlined in Table 4 are improved [Wang 2018, Strategy C].

In our primary variable selection strategy, we will 1) define a list of potential covariates *a priori* as described in Section V.F; 2) specify one or several models using all or a manually selected subset of the covariates; 3) assess model diagnostics, including but not limited to diagnostic assessments described in Table 4; and 4) refit models in response to diagnostic results providing information about over-fitting, positivity violations, or covariate instability. Possible strategies for improving model fits may include collapsing sparse or collinear variables into composite variables where appropriate, or removing variables from the model if covariate balance is maintained between DEX+ and referent groups. We may also consider automated variable selection strategies such as HDPS or LASSO if they improve model fits relative to manual variable selection.

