3	Confirm baseline confounder balance	We will confirm that the distributions of all potential confounders are balanced for DEX+ vs. referent. Covariate balance will be defined as absolute standardized differences (ASDs) $\leq 0.10$ [Austin 2009].  Although variables with balance prior to PS matching may be removed from the PS model, balance of these variables will still be confirmed after PS matching.  If there is a variable with a small residual imbalance ( $0.10 \leq ASD \leq 0.20$ ), balance may be deemed acceptable if the variable does not predict the outcome among the referent group (defined as an ASD $< 0.10$ when comparing the risk of the outcome in those with the variable vs. those without it). Evaluation of imbalance in outcome prediction will only be conducted once at the end of the diagnostic phase if all other diagnostic criteria are met.	
4	Confirm models are not overfit	We will confirm that all models contain approximately 12 exposed subjects or more per covariate	

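### The Table 4 overfitting check counts only DEX+ patients, so in DEX+ vs MPRED+ it does not respond if MPRED+ is the smaller group

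*Protocol*

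**What the plan says.** The only numerical overfitting criterion in the Protocol is Table 4 row 4 (section VI.B): "We will confirm that all models contain approximately 12 exposed subjects or more per covariate". It covers every PS model.

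Section V.B defines the exposure: "The primary exposure of interest is new (incident) initiation of systemic DEX". Table 1 (section III) agrees, listing DEX+ as the exposure and CSI-, DEX- and MPRED+ as referents. Section VI.A fits a separate main-effects logistic model of DEX+ against each referent.

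The referent groups are formed in two ways (section V.C.2):

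- **CSI- and DEX-** are risk-set sampled, with at least one referent per DEX+ patient. For CSI-, ratios of 1:1 to 1:4 "will be considered to select up to 4 non-user referent patients for each exposed". The DEX- text has the same structure: "For each new user of DEX, at least 1 patient who has not (yet) used DEX as of the DEX patient's index date".
- **MPRED+** is not sampled. The cohort is "all patients who begin use of DEX or MPRED between the admission date" and the end of the index window, and no ratio is stated.

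Two statements bear on the likely balance of DEX and MPRED. Section II.B says "DEX utilization has substantially increased in the US since June 2020". Section V.C.1 notes that MPRED use was higher earlier in the pandemic and, for this comparison, says "we may consider delaying the cohort entry to start in May or June".

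**The concern.** In a binary logistic model, the smaller outcome class limits how many coefficients can be estimated stably. Adding patients to the larger class helps less and less. A rule that counts one named group works only when that group is the smaller one or the two are equal.

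The sampling design secures this for CSI- and DEX-. Nothing secures it for MPRED+. If MPRED+ is the smaller group, row 4 can be met by a model with too few MPRED+ patients for its terms.

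Such a model would have unstable PS coefficients. It would also exaggerate the separation between the groups, which may cost matches within the 1% caliper. Secondary II is the only active-comparator analysis. No risk-set matching is described for it, so its confounding control rests mainly on this model.

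**Working it through.** The 12 is a chosen threshold. The Protocol derives no sample size or event count from it, so there is no planned figure to reproduce. The check compares what row 4 measures with what limits the model.

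**Inputs**

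- Threshold: about 12 per covariate (Table 4 row 4).
- DEX+ = 1,840 (Appendix A.2, Table A.2). This comes from an exploration cohort already matched against DEX-. It is not the final cohort and not the Secondary II cohort, and is used only for scale.
- MPRED+: no count in the Protocol. Assumed 1,840, 920, 460 and 184.
- Model terms k: not fixed in the Protocol. Assumed 60, with a range of 40 to 100.

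**Step 1: which group limits each model.** For CSI- and DEX-, the referent count is at least the DEX+ count, so min(DEX+, referent) = DEX+ and row 4 counts the right group. For MPRED+, the minimum can be either group.

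**Step 2: row 4 against the smaller-group count.** Row 4 = DEX+/k = 1,840/60 = 30.7. The smaller-group count = min(DEX+, MPRED+)/k. The information on a coefficient is, near the null, proportional to DEX+ × MPRED+ / (DEX+ + MPRED+).

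| DEX+ | MPRED+ (assumed) | Row 4 | Smaller group per covariate | Information factor |
|---|---|---|---|---|
| 1,840 | 1,840 | 30.7 | 30.7 | 1,840×1,840/3,680 = 920 |
| 1,840 | 920 | 30.7 | 15.3 | 1,840×920/2,760 = 613 |
| 1,840 | 460 | 30.7 | 7.7 | 1,840×460/2,300 = 368 |
| 1,840 | 184 | 30.7 | 3.1 | 1,840×184/2,024 = 167 |

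Row 4 stays at 30.7 while the information factor falls from 920 to 167. At 1,840 DEX+ patients, row 4 allows 1,840/12 = 153 covariates however few MPRED+ patients there are.

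**Step 3: where the two counts disagree.** Twelve per covariate in the smaller group needs 12k patients. For k = 40, 60, 80 and 100, that is 480, 720, 960 and 1,200. Against 1,840 DEX+ patients, MPRED+ falls short below 26%, 39%, 52% and 65% of the DEX+ count respectively.

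**Step 4: simulation.** There were 60 independent normal covariates, ten of them shifted by 0.15 SD between groups, and 60 replicates. A calibration slope of 1 means no overfitting.

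| DEX+ | MPRED+ | Row 4 | Apparent / validation AUC | Slope |
|---|---|---|---|---|
| 1,840 | 1,840 | 30.7, pass | 0.650 / 0.615 | 0.75 |
| 1,840 | 920 | 30.7, pass | 0.657 / 0.608 | 0.67 |
| 1,840 | 460 | 30.7, pass | 0.672 / 0.599 | 0.55 |
| 1,840 | 184 | 30.7, pass | 0.710 / 0.583 | 0.36 |
| 460 | 1,840 | 7.7, fail | 0.671 / 0.601 | 0.56 |
| 184 | 1,840 | 3.1, fail | 0.707 / 0.582 | 0.37 |

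The last two rows mirror the two above them. Overfitting is almost the same in each pair, but row 4 flags it only when DEX+ is the small group.

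**The case against.** **MPRED+ may not be smaller.** The Protocol gives time trends, not totals, and the later start is optional and would remove only the first month or two. If MPRED+ is at least as large as DEX+, row 4 counts the right group. This stands, so the point is conditional.

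**The tick opens no gate for this comparison.** A reader might infer that the study could move to the inferential phase on a false pass. The Protocol does not support that. Section VI.B ties progression to the primary objective in the overall cohort, and section VI.A promises only an attempt at the criteria for the secondary objectives. This limits the consequence. But a criterion aimed at the wrong group is a poor guide to that attempt.

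**Other safeguards exist.** Row 2 inspects overlap and row 3 requires balance after matching. Section VI.A does not limit diagnostics to Table 4 and allows refitting for overfitting or unstable covariates. This is real but partial protection: none of these counts subjects per covariate.

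**Harm to the estimate is not demonstrated.** The simulation shows overfitting of the PS, not bias in the hazard ratio, loss of matches or residual imbalance. Nor should unstable weights be inferred, since the plan matches and does not weight. This also stands.

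**The rule of 12 is itself rough.** In the simulation, 15.3 per covariate in the smaller group still gives a slope of 0.67, and 30.7 gives 0.75. Counting the smaller group makes the check respond to the right number. It does not certify the model.

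**Conclusion.** Row 4 is worded for the two risk-set-sampled comparisons and does not carry over to DEX+ vs MPRED+. If MPRED+ is the smaller group there, the check does not respond to the group that limits the model.

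The figures of 15.3, 7.7 and 3.1 against a constant 30.7 are illustrative. They rest on an exploratory DEX+ count, an assumed 60 terms and assumed MPRED+ sizes. A reader might conclude that the Secondary II model is in fact overfit, or that row 4 would sit exactly at 12 while MPRED+ has only a few patients per term. The Protocol supports neither: it gives no MPRED+ count and no final number of covariates, and the second reading also needs DEX+ to lie at the bare minimum.

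The effect is confined to Secondary II and its subgroups. It would matter more if PS models were fitted within subgroups, as section VI.A permits, because the groups would then be smaller. This is a minor correction to a stated rule, worth making because it is so cheap.

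**What to change.** Reword Table 4 row 4 to require *approximately 12 or more subjects in the smaller of the two treatment groups per model covariate*.

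The limiting group for the primary objective and Secondary I stays DEX+, so nothing changes there. For Secondary II, the model may have to carry fewer terms if MPRED+ proves small. Section VI.A already allows sparse variables to be collapsed or removed, and dropped variables would still be checked for balance under row 3. No additional data are needed.

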**C. Inferential phase**

The *Inferential Phase* begins after all diagnostic criteria are satisfied or the protocol is publicly posted, whichever is later. To prevent changes to the underlying patient or event-level data from occurring when new data are available, the data cut will be locked at the start of the *Inferential Phase*.

For the primary outcome of 28-day mortality, the following will be reported in the overall cohort and within each subgroup of interest before PS matching and after PS matching:

- Rates reported per 1,000 person-days, overall and for each subgroup.
- Hazard ratios (HR) and corresponding 95% CIs for the effect of DEX+ compared to each referent (CSI-; DEX-; MPRED+) overall and for each subgroup using PS-matched cohorts. If residual imbalance ( $0.10 \leq ASD \leq 0.15$ ) remains after PS matching, Cox proportional hazard models may be specified to adjust for any imbalanced confounders. Otherwise, HRs will be unadjusted.

In subgroups that do not achieve the minimum sample size requirements, results will be presented in the context of an estimation framework rather than a formal hypothesis testing framework, and findings should be interpreted with caution.

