**B. Diagnostic phase and checklist**

The diagnostic phase checklist developed for this study is shown in Table 4 below. Upon each data update, the diagnostic results will be executed and discussed with the FDA RCA team until there is consensus that we have satisfied the necessary criteria for the primary objective in the overall cohort to progress to the *Inferential Phase*. Sample size calculations are part of the iterative cycle of the *Diagnostic Phase* rather than fully completed in advance to allow consideration of new study findings (in addition to the RECOVERY trial [RECOVERY 2020]) that impact the assumptions underlying the sample size calculations. Treatment effects will not be estimated during the *Diagnostic Phase*. All treatment effects will be examined during the *Inferential Phase* after the data is locked and propensity score models are finalized.

Table 4: Diagnostic checklist to complete prior to progression to the inferential phase

#	Diagnostic	Description	✓
1	Confirm adequate sample size	Adequate sample size will be defined as the minimum sample size required to achieve 80% power using a 2-sided 95% confidence interval (0.05- alpha ) assuming a hazard ratio of 0.8 and the baseline risk of 28-day mortality in the primary referent CSI- group estimated as the risk in the RSS-matched CSI-group prior to PS matching (since the baseline risk is otherwise unknown in the	

		US patients hospitalized for COVID-19). Further confirm which subgroups of interest achieved minimum sample size for formal hypothesis testing.	
2	Confirm positivity of variables	PS distributions will be visually inspected, and overlap in all areas of the PS distributions will be confirmed.	

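### The Cox-adjustment option in VI.C stops at ASD 0.15, which conflicts with VI.A for the secondary comparisons and leaves larger imbalances in DEX+ vs CSI- severity subgroups with no Cox remedy

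*Protocol*

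**What the plan says.** Section VI.C governs the HRs for DEX+ against CSI-, DEX- and MPRED+, overall and by subgroup. If a residual ASD of 0.10 to 0.15 remains after PS matching, "Cox proportional hazard models may be specified to adjust for any imbalanced confounders. Otherwise, HRs will be unadjusted".

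Section VI.A deals with unmet balance criteria in the secondary objectives differently: "strategies such as covariate adjustment to control for residual imbalance may be used in the event that some criteria are not satisfied". It gives no upper ASD limit.

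Table 4 item 3 sets balance at ASD 0.10 or less. For 0.10 to 0.20, "balance may be deemed acceptable if the variable does not predict the outcome among the referent group". This is an acceptance screen and does not say when to adjust.

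The checklist controls progression through "the necessary criteria for the primary objective in the overall cohort". Subgroups and secondary comparisons have no gate of their own.

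On subgroup matching, VI.A says "Referent groups for subgroup analyses will be identified using the overall PS model", with the PS fitted "based on main effects of the independent covariates without interaction terms". A PS fitted within subgroups is optional: "This modeling strategy may be used for the final analysis if diagnostic criteria outlined in Table 4 are improved".

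**The concern.** A rule for residual imbalance should not lapse as the imbalance grows. Read literally, VI.C permits correction in the 0.10 to 0.15 band and prescribes an unadjusted HR above it, with no reason given for 0.15.

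There are two consequences.

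- **Secondary comparisons (DEX-, MPRED+).** VI.A and VI.C give different answers for the same ASD above 0.15. The analyst would have to choose between them, possibly with treatment effects already in view, which the staged design is meant to prevent.
- **Subgroups of the primary comparison (CSI-).** VI.A's uncapped option is written for secondary objectives, so VI.C's ceiling stands alone. A severity subgroup can reach analysis with an ASD above 0.15 and no Cox remedy.

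HRs by severity are listed as key subgroup results for all three referents, so the gap touches results that will be read.

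**Working it through.** The protocol states no figure to reproduce here. The check compares the rules and then asks how often, and by how much, the gap would matter.

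**1. The rules side by side**

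| Setting | ASD 0.10-0.15 | ASD 0.15-0.20 | ASD above 0.20 |
|---|---|---|---|
| Primary, overall | Cox adjustment optional | Passes only if non-predictive (Table 4) | Fails the diagnostic |
| Secondary comparisons | Optional (VI.A and VI.C) | VI.A: optional; VI.C: unadjusted | VI.A: optional; VI.C: unadjusted |
| Subgroups of DEX+ vs CSI- | Optional (VI.C) | Unadjusted (VI.C) | Unadjusted (VI.C) |

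The primary overall HR is largely protected. The gap lies in the last two rows.

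**2. How often a covariate exceeds 0.15 by chance**

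Assume that subgroup balance is as good as randomisation. The standard error (SE) of a standardized difference is then about sqrt(2/n) with n per arm, and P(ASD > c) = 2 × (1 − Φ(c / sqrt(2/n))).

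| n per arm | Source | SE | P(ASD > 0.10) | P(ASD > 0.15) |
|---|---|---|---|---|
| 62 | Table A.3, IMV | 0.180 | 57.8% | 40.4% |
| 417 | Figure A.5, 834 IMV patients, assumed 1:1, before PS matching | 0.069 | 14.9% | 3.0% |
| 592 | Table A.3, oxygen only | 0.058 | 8.5% | 1.0% |
| 1,098 | Table A.3, no oxygen | 0.043 | 1.9% | 0.04% |

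**3. What Table A.3 shows**

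ASD = |p1 − p2| / sqrt((p1(1 − p1) + p2(1 − p2)) / 2). In IMV (62 vs 62, DEX+ vs DEX-, from an earlier data cut), five characteristics exceed 0.15:

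- end-stage or severe kidney disease, 2 vs 0: 0.258
- age 70-79, 12 vs 7: 0.225
- male sex, 38 vs 32: 0.196
- HIV, 1 vs 0: 0.181
- severe liver disease, 1 vs 0: 0.181

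Three of the five rest on one or two patients. Fisher p is at least 0.32 for all five. Mean age is balanced: (63.35 − 62.63) / sqrt((10.14² + 10.89²) / 2) = 0.068. The largest tabulated ASD is 0.081 in no oxygen and 0.073 in oxygen only.

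**4. Effect of one such covariate on the HR**

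The bias factor is (1 + q(RR − 1)) / (1 + p(RR − 1)), with prevalence p from 10% to 50% in one arm, q set by the ASD, and an assumed mortality ratio RR.

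| ASD | RR 1.5 | RR 2 | RR 3 |
|---|---|---|---|
| 0.15 | 2.4-3.1% | 4.5-5.4% | 7.5-9.0% |
| 0.20 | 3.2-4.1% | 6.2-7.3% | 9.9-12.2% |

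**5. Against precision**

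SE of log HR = 2/sqrt(deaths), 1:1. Assumed mortality is 25.7% (RECOVERY control arm) to 36% (routine-care arm of DEXA-ARDS), both quoted in section II. Applying either to IMV is an assumption.

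- 62 pairs: 124 × 0.257 = 31.9 to 124 × 0.36 = 44.6 deaths, SE 0.354 to 0.299, 95% CI factor 2.0 to 1.8. A 6-12% shift is about 0.2-0.4 SE.
- 834 patients: 214 to 300 deaths, SE 0.137 to 0.115, CI factor 1.31 to 1.25. The same shift is about 0.4-1.0 SE.
- Deaths needed for HR 0.8 at 80% power: 4 × (1.96 + 0.8416)² / ln(0.8)² = 630.5, so about 631. Both IMV sizes fall short.

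**The case against.** Several objections have weight.

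- **The wording is permissive.** The option says adjustment may be specified, and it refers to any imbalanced confounder. That could take in one above 0.15, but at best only when another covariate falls inside the band. The closing sentence prescribing unadjusted HRs is not permissive.
- **Risk-set sampling already does much of the work.** For the CSI- and DEX- comparisons, Table 2 matches on severity, age within 3 years, sex, comorbidity category, calendar date and time since admission. This stands and narrows the concern. Later PS matching can loosen it, as the sex split in Table A.3 shows, and other covariates depend on the PS alone.
- **A ceiling could mean that small residuals are patched and larger ones prompt a refit.** VI.A does provide for refitting. But it is optional for subgroups, no gate forces it, and VI.C does not say that exceeding 0.15 triggers it. Table 4 item 4 ("We will confirm that all models contain approximately 12 exposed subjects or more per covariate") would also hold a PS model in 62 exposed patients to about 5 covariates (62/12).
- **The example comes from the wrong comparison.** This is correct. Table A.3 is DEX+ vs DEX-, where VI.A already permits adjustment, and no CSI- subgroup data are shown.

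A reader might infer from Table A.3 that the IMV subgroup is materially confounded and that the protocol leaves it so. The documents do not support that. The values are compatible with chance, come from an earlier cut, and show only that ASDs above 0.15 can occur. Nor is Table 4's 0.20 bound a third adjustment rule that contradicts the other two, because it serves a different purpose.

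**Conclusion.** The point holds as a minor defect. Sections VI.A and VI.C conflict for the secondary comparisons. For subgroups of DEX+ vs CSI-, VI.C's ceiling leaves an ASD above 0.15 with no Cox remedy. The textual conflict is certain.

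The practical size is limited. The gap is likely to bite only in a small IMV stratum, at about 40% per covariate with 62 per arm and 3% or less from 417 per arm upward. One covariate at ASD 0.20 with an assumed mortality ratio of 2 to 3 would move the HR by about 6-12%. That is well inside the confidence interval at 62 pairs and up to about one SE with 834 patients. Such a stratum would probably be presented as estimation only under VI.C. The primary overall HR is little affected.

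These figures assume chance-level balance, 1:1 matching, and mortality and mortality ratios that the protocol does not give for this subgroup.

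**What to change.** Delete the 0.15 upper limit in VI.C and state one rule in both VI.A and VI.C:

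- Potential confounders with post-match ASD above 0.10 in the cohort or subgroup analysed may be adjusted for in the Cox model, for primary and secondary comparisons alike.
- Variables accepted as non-predictive under Table 4 item 3 are excepted.
- An ASD above 0.20 in the primary overall cohort remains a failed diagnostic.
- Where deaths are few, limit the terms to the main prognostic imbalanced covariates. At roughly 10 deaths per term, 32-45 deaths support 3-4 terms.
- Report the unadjusted HR alongside.

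Entering the overall PS as a single Cox term is not a useful substitute. Subgroup referents are already matched on that score within a ±1% caliper, so it would correct little.

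The cost is a wording change, a few extra Cox terms and a slight loss of precision in small subgroups. No new PS model or data are needed. The change should be made before the Inferential Phase begins.
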